## 10.1 Safety Endpoints

### 10.1.1 Infection and Irritation

Infection and irritation are the most serious risks identified for the NPS, and as such the absence of both serves as a primary safety endpoint for the study. The implant sites will be monitored by visual inspection of the wound margin, verbal survey of the subject, and neurologic exam.

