- Infection could occur after surgery, including meningitis (which has the potential to cause brain damage or hearing loss). The expected frequency of these complications is low: the rate of infection in similar neurosurgeries suggests that the rate of infection in this study may fall between 1.7% and 9.1%, with most reports from the last decade within the range 1.7% to 4% (79-85, 87-90). After the implantation surgery, the subject will receive critical care for a minimum of 1-2 days in the hospital. The patient will receive 24 hours of IV antibiotics post-op. During this time, the subject will be closely monitored for any signs of systemic infection and infection around the wound. If any infection occurs, the subject will receive immediate, appropriate clinical treatment.
- Short-term pain in the head or neck might occur after surgery. The expected frequency of these complications is moderate. The subject will likely experience discomfort in the head and neck due to the nature of the surgery. This pain will be short-term, and should dissipate during the post-operative critical care period, or during the healing period. The attending physician will review each subject's condition individually to determine whether the discomfort requires pharmacological intervention or other response.
- Allergic reaction to the implanted devices is possible. The expected frequency of this complication is low. The NeuroPort Arrays are manufactured using biologically-safe materials, and have a documented history of being implanted both acutely and chronically without incidence of allergic reaction. The NeuroPort Arrays are cleared under 510(k) approval for implantations of less than 30 days. Subjects will be monitored closely during surgery, during the post-operative critical care period, and throughout the study to watch for signs of allergic reaction to the implanted device. If symptoms occur, they will be evaluated by the attending physician, who will determine the proper response (ranging from medication to explantation and exit from the study).

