- Discomfort or lack of healing of the skin area could occur at or around the site of the implanted percutaneous connector. The expected frequency of occurrence for this complication is moderate. In studies of bone-anchored hearing aids, severe skin irritation or infection has been reported in 1.0% to 5.0% of all observations (68-70). However, low-to-moderate skin irritation or infection (i.e., treatable via medication) has a higher rate of incidence – 5.1% to 14.0% (68, 71). The wound site will be carefully monitored at all stages of the study, and the subject questioned, to detect signs of discomfort or inadequate healing. Such symptoms and conditions will be treated appropriately and immediately at the direction of the attending physician.
- Tissue damage and histological responses could lead to functional deficits and increased long-term risk of neurological disorder. The expected frequency of these complications is low. When subdural electrode strips are placed to localize epileptogenic tissue, transient neurological deficits have been reported in 5.6% to 11.1% of cases (87, 89). For tissue resection, rates of transient neurologic deficit increase to 8.6% to 30% (90, 91). Permanent neurologic deficits due to stereotactic electrode placement are rare, reported at 0.6% to 1.5% (85, 87, 91). The NeuroPort Arrays are small (4 mm x 4 mm) and short (electrodes are 1.5 mm in length), and will displace or damage small amounts of tissue. During the study, the subject will be monitored on a daily basis by caregivers, and evaluated regularly by physicians, to watch for seizures, loss of function, change in function or behavior, or any other signs of complications. If any appearing symptoms are specified as exit criteria, the patient will be explanted and exit the study.

Otherwise, the attending physician will judge whether conditions are serious enough to warrant explantation.

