### 3.7 Healing Period

Following the in-hospital critical care period, the subject will be released to return home. Wounds will be monitored on a weekly basis. Wound care instructions will be provided to the patients and their caregivers. The healing period will last 2 weeks, during which the subject will receive no less than two follow up visits with the

neurosurgeon and neurologist while the wound site heals. During this period, the NPS may be tested briefly for functionality, but no study sessions will occur.

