10.0 Criteria for Evaluation and Endpoint Definitions

The objectives of this study are to evaluate the safety and effectiveness of the NPS. Each of these objectives will be measured quantitatively as defined in Table 10-1 and described in this section.

Table 10-1. Safety and Effectiveness Endpoints

Objective	Hypothesis	Method of Evaluation	Time of Assessment	Comparisons Made
To evaluate the safety of the NPS implant	Primary endpoint – implantation will not be associated with infection or irritation	Inspection of subject's scalp for evidence of reddening or discharge; review of new symptoms including possible fever, headache, visual or auditory changes, or change in mood or behavior; serial neurologic exams	Immediately after implantation and weekly thereafter	The condition of the area will be compared with its condition on previous visits  History will be obtained regarding new symptoms  Neurologic exam will be compared to baseline neuro exam
	Secondary endpoint – the Severe Adverse Event (SAE) rate will not rise above 1% for any study subjects.	The SAE rate will be calculated as the number of SAEs per implant-days.	The SAE rate will be available on a daily basis throughout the study.	The SAE rate will be continuously compared to the 1% threshold level.
To evaluate the effectiveness of the NPS	Primary endpoint – patient control over the end effector (virtual or physical), as measured by accuracy, will be significantly greater than chance when using the NPS	Calculated by the NPS computer apparatus	At the end of every study session	Assessments will be compared with chance
	Secondary endpoint – Action Research Arm Test (ARAT) scores will improve over the course of the trial when controlling the virtual or physical robotic arm	ARAT administered by occupational therapists	At 10-week intervals starting at week 3.	Scores will be compared to the baseline, i.e., the first score from week 3.
	Tertiary endpoint – using the NPS with either a virtual or physical end effector will result in significant increases in the subject's quality of life	Quality of Life Inventory (QOLI) administered by the NPS operator	During prescreening (baseline) and every month subsequent to implantation	Monthly QOLI score will be compared against baseline

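### Does an ungraded primary safety endpoint of no infection or irritation in two subjects need redefinition?

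*Protocol*

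**What the plan says.** Table 10-1 states the primary safety hypothesis as "implantation will not be associated with infection or irritation", and 10.1.1 adds that "the absence of both serves as a primary safety endpoint for the study". The synopsis confines the outcome variable to infection or irritation at the implant site. The method column of Table 10-1 looks for "evidence of reddening or discharge; review of new symptoms including possible fever, headache" and other changes. The timing is "Immediately after implantation and weekly thereafter". The comparison column sets the site against its state at earlier visits and the neurological examination against baseline. The next row of the table is the secondary safety endpoint, an SAE rate compared continuously with a 1% threshold.

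On healing, 3.7 says "The healing period will last 2 weeks". On expected findings, 1.4.2 says of post-operative pain that "The subject will likely experience discomfort in the head and neck due to the nature of the surgery". Of discomfort or poor healing at the connector it says "The expected frequency of occurrence for this complication is moderate".

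Section 2.1 ties the safety hypotheses to the endpoints in 10.1. Section 13.5, with the same text in the SAP, treats the safety objective as met by implanting the device in two people and monitoring their health. Section 13.4 describes the power as weak and says the outcomes will inform whether larger studies are justified.

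**The concern.** Read literally, the endpoint is all-or-nothing. A treatable superficial infection and an infection that forces explantation would count the same. Inspection starts straight after a craniotomy, when some redness is to be expected, and no rule turns the comparison with earlier visits into met or not met. The very first check has no earlier post-implant visit to compare with.

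The primary safety hypothesis could therefore be refuted by something trivial. In the other direction, 13.5 could be taken to declare safety established whatever is observed. Since the results will be used to decide on larger studies, a misreading either way would matter.

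**Working it through.** The documents give no power, error rate or threshold for this endpoint, so there is no planned figure to reproduce. The check has three parts.

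**1. What can count as an event.** Headache and fever stand in the method column of Table 10-1. They are signs to be reviewed, not events in themselves. The synopsis limits the outcome to the implant site, and 8.2.8.2 and 8.2.8.3 list irritation, soreness, pain and headache as separate terms. Post-operative head and neck pain is therefore neither infection nor irritation. What remains is local skin reaction and infection. For the skin, the comparison with earlier visits allows a change-based reading, under which settling post-surgical redness need not count.

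**2. Where severity is captured.**

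| Provision | Section |
|---|---|
| All adverse events recorded in the case history; device-associated ones classed serious or mild | 8.2.3 |
| Serious event defined | 8.2.1 |
| Serious infection at the connector is a withdrawal criterion | 5.3 |
| Minor or superficial infection treated and monitored | 1.4.2 |
| SAE rate against 1% | Table 10-1, 10.1.2 |

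The serious/minor distinction will be available for each event in each subject.

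**3. How much the numbers can say.** Inputs: n = 2; hearing-aid rates from 1.4.3 of 5.1–14.0% (low or moderate) and 1.0–5.0% (serious). Assume these are per-subject risks and do not overlap. The chance of at least one event is 1 − (1 − p)².

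- Low/moderate only: 1 − 0.949² = 9.9%; 1 − 0.86² = 26.0%.
- Serious only: 1 − 0.99² = 2.0%; 1 − 0.95² = 9.8%.
- Both (6.1% to 19.0%): 1 − 0.939² = 11.8%; 1 − 0.81² = 34.4%.

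Low/moderate share of all events: 5.1/(5.1 + 5.0) = 50% to 14.0/(14.0 + 1.0) = 93%.

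These results depend heavily on the assumptions:

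- *Post-operative infection.* Section 1.4.3 also expects 1.7–4.0%. If that is added as serious and non-overlapping, the low end of the minor share falls to 5.1/(5.1 + 5.0 + 4.0) = 36%. The any-event chance becomes 1 − (1 − 0.078)² = 15.0% to 1 − (1 − 0.23)² = 40.7%.
- *Denominator.* Section 1.4.2 words the rate as "severe skin irritation or infection has been reported in 1.0% to 5.0% of all observations". If it applied to each of 2 × 53 = 106 weekly checks, treated unrealistically as independent, the chance would be 1 − 0.99¹⁰⁶ = 65.5% to 1 − 0.95¹⁰⁶ = 99.6%.

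The exact binomial limits do not use these rates:

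- 0 of 2: one-sided 95% upper limit 1 − 0.05^(1/2) = 77.6%; two-sided 1 − 0.025^(1/2) = 84.2%.
- 1 of 2: 1.3% to 98.7% (two-sided).
- 2 of 2: 15.8% to 100% (two-sided).

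Whatever is observed, the estimate is nearly uninformative about the population rate, and regrading the endpoint does not change that.

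**The case for a change.** The best case for a change is that Table 10-1 promises quantitative measurement, yet this row has no decision rule, while the SAE row has a threshold. The severity classes already exist, so tying them to the endpoint would cost only a few lines. Section 13.4 calls the power weak without saying how weak, and 13.5 names neither infection, irritation nor the SAE threshold.

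Part of this stands. Irritation has no case definition, and the comparison with earlier visits has no stated rule, including in the healing period. Analysts will have to settle both.

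The proposed remedy does not reach either gap. Reporting events as serious or minor would leave the hypothesis as it is, so a minor event would still refute it, and irritation would still be undefined. The split can be made from records that 8.2.3 already requires.

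On 13.5, the stated objective is to evaluate safety, and implanting and monitoring two subjects does that. Section 2.1 is where the hypotheses are tied to 10.1, so the two sections do not contradict each other. An exact interval for 0 of 2 can be given in any report without amending the plan.

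**Conclusion.** No change is needed. The missing grade and decision rule are a gap in detail that analysts of a two-subject feasibility study can fill sensibly: describe each infection or irritation event by subject, timing and serious or mild class. The plan already disclaims conclusions about absolute safety, so no conclusion it intends to draw depends on a sharper endpoint. The limitation is sample size: even a clean result leaves a per-subject rate up to 77.6% possible (one-sided 95%), with or without a redefinition.

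This rests on events being recorded and classified as 8.2.3 requires; the clinical-note forms were not available to check. The hearing-aid probabilities are illustrations only. In particular, a claim that most failures would be minor is not supported, because that share can fall to 36% once the protocol's own post-operative infection rate is included.

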### 10.1.2 SAE Rate

The severe adverse event (SAE) rate is the secondary safety endpoint. The indicated SAE rate threshold, at 1% SAEs per implant-days, was established based on literature describing adverse events for similar procedures (107, 108).

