#### 1.4.1 Risks Associated with Related Clinical Procedures

Components of this study which generate the majority of risk to the subject include the implantation and explantation surgeries, and the percutaneous connector. Given the early stage of clinical development for the device investigated in this study, it may be useful to examine other procedures and operations which include similar components. For example, bone-anchored hearing aids (BAHAs) rely on a titanium fixture similar to the titanium percutaneous component (the percutaneous connector) used in this study; rates of infection for BAHA devices have been reported in the range of 1.0% to 5.0%, with other complications (<1%) including persistent pain, granulation tissue, and persistent bleeding (68-71). Infections which occur as a result of neurosurgery are potentially severe, but have a low incidence rate of 1.7% to 2.6% in the United States (72-78). Placement of foreign bodies (specifically, shunts), CSF leakage, age, and duration of surgery have all been implicated as being significantly associated with surgical site infections for craniotomies and other neurosurgeries (73-75, 77). Prophylactic antibiotics may play a role in mitigating the risk of infection (73). Anticipated adverse events associated with implantation of leads for epilepsy localization procedures include hemorrhage (0.8% to 2.5% of patients), infection (1.8% to 9.1%) and permanent neurological complications such as hemiparesis, aphasia, apraxia, Gerstmann syndrome, and other sensory and motor deficits (0.6% to 1.5%; transient deficits occur somewhat more frequently). Resection of epileptic tissue is associated with hemorrhage (0.7%) and infection (1.0%) and neurological deficits (about 3.3%), such as language, visual field, and motor deficits. Deep Brain Stimulation (DBS) systems are associated with hemorrhage (1.1% to 3.9%), infection (1.7% to 4%), and neurological deficits such as hemiparesis (about 1.1% to 16% of patients) (79-85).

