### 1.5 Central Hypotheses

We hypothesize the following regarding the safety of the device:

- (1) Implantation will not be associated with infection or irritation;
- (2) The Severe Adverse Event (SAE) rate, calculated as the number of SAEs per implant-day, will not rise above 1% for any study subjects.

We hypothesize the following regarding the effectiveness of the device:

- (1) Control over virtual and physical end effectors, as measured by accuracy, will be significantly greater than chance when using the NPS;
- (2) Action Research Arm Test (ARAT) scores will improve over the course of the trial when controlling virtual or physical end effectors
- (3) Using the NPS with either virtual or physical end effectors will result in significant increases in the subjects' quality of life.

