### 3.0 Study Design

#### 3.1 Overview

A prospective, longitudinal, single-arm early feasibility study will be used to examine the safety and effectiveness of using the NPS with physical and virtual end effectors. Figure 3-1 illustrates the progression of a subject through the study from recruitment to study exit. Two subjects will be enrolled, each implanted with the NPS for a period of 53 weeks. The study is expected to take two years in total.

At the end of the study period, it is expected that the subject will have the device removed, continue with follow-up care, and end all study-related activities. However, it may be necessary to evaluate a continuation of the study period if the subject expresses a desire to keep the device. The subject, caregiver, clinical team, and research support team will consult to determine whether it is safe and feasible to do so. If the subject and team agree to allow the device to remain implanted, a new informed consent for long-term follow up will be obtained, and the appropriate oversight bodies (i.e., FDA, IRB, and monitoring organization), will be notified.

All surgical and medical care will be provided according to best medical practice, including protocol activities and care provided in an emergent situation.

A schedule indicating the expected time required for each step of the study is listed in Table 3-1. Because the Recruitment phase depends on the availability and qualifications of an as yet unknown person, there is no specific amount of time listed.

Table 3-1. Study time course

Study Week	Study Phase	Section
N/A	Recruitment	3.2
0	Informed Consent	3.3
0	Eligibility	3.4
1	Baseline/pre-implant	3.5
2	Device implantation	3.6
2 – 3	Healing period	3.7
4 – 53	Study period	3.8
54	Device explantation	3.8.3
54 – 66	Follow-up care	4.0

[figure not shown]

Figure 3-1. Participant progression through the proposed study.

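### The 1% SAE limit is per implant-day, which is 3.71 SAEs per subject over 53 weeks; the complication rates quoted in section 1.4 are cumulative, and nothing in the plan links the two.

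*Protocol*

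**What the plan says.** The second safety hypothesis in Protocol section 1.5 reads: "The Severe Adverse Event (SAE) rate, calculated as the number of SAEs per implant-day, will not rise above 1% for any study subjects". Section 2.1 repeats the 1% without a unit. Table 10-1 in section 10.0 makes it the secondary safety endpoint, says the rate is available daily, and adds: "The SAE rate will be continuously compared to the 1% threshold level". Section 10.1.2 gives the origin of the figure: "The indicated SAE rate threshold, at 1% SAEs per implant-days, was established based on literature describing adverse events for similar procedures". Two references are cited there, but no source rate, time unit or conversion is shown.

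Exposure comes from section 3.1: "Two subjects will be enrolled, each implanted with the NPS for a period of 53 weeks".

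The complication rates for related procedures are in section 1.4. An example from 1.4.1 is "Deep Brain Stimulation (DBS) systems are associated with hemorrhage (1.1% to 3.9%), infection (1.7% to 4"%), in a paragraph that counts patients. In 1.4.2 the denominator changes: "severe skin irritation or infection has been reported in 1.0% to 5.0% of all observations". Transient deficits are given per case, and CSF leakage is given for neurosurgical procedures.

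The SAP reproduces Protocol section 13 and adds nothing on the SAE limit.

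**The concern.** A limit of 1% reads naturally as one patient in a hundred, and it resembles the single-digit percentages quoted throughout section 1.4. It is a different quantity: a daily event rate that accumulates over a year of implantation. Read at the end of that year, it tolerates several SAEs in one person.

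This is the only safety hypothesis with a numerical limit, and section 13.4 says the outcomes will inform whether larger studies are warranted. A report that the SAE rate stayed at or below 1% could be taken as agreement with the low complication rates in section 1.4 when a subject had in fact had three SAEs. The plan also does not say whether the running rate or the final rate settles the endpoint, and the two can disagree for the same subject.

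**Working it through.** **Inputs.** Limit: 0.01 SAEs per implant-day, applied to each subject (1.5, Table 10-1, 10.1.2). Exposure: 53 weeks (3.1), so 53 x 7 = 371 days. Table 3-1 (implant in week 2, explant in week 54) and Table 18-1 (weeks 0 to 52) suggest 52 x 7 = 364 days instead. The plan's 1% cannot be reproduced, because no derivation is given.

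**1. The limit as a count.** 0.01 x 371 = 3.71 SAEs per subject (0.01 x 364 = 3.64). Final rates: 3/371 = 0.81% passes and 4/371 = 1.08% fails. The cut between three and four is the same on 364 days.

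**2. The running comparison.** The k-th SAE on day t exceeds the limit when k/t > 0.01, that is, when t < 100k. The first SAE breaches before day 100, the second before day 200 and the third before day 300. A fourth always breaches, since 400 > 371.

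| SAE days | Running rate at each SAE | Final rate | Running reading | Final reading |
|---|---|---|---|---|
| 50 | 1/50 = 2.00% | 1/371 = 0.27% | fails | passes |
| 150, 250, 350 | 0.67%, 0.80%, 0.86% | 3/371 = 0.81% | passes | passes |

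**3. Setting the limit beside section 1.4.** The protocol states no overall expected SAE rate, so these sums are mine and only illustrative. They add selected complications as if each were a separate SAE, and they ignore differences in denominator.

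- Low ends: bleeding 0.8 + infection 1.7 + permanent deficit 0.6 + serious connector infection 1.0 = 4.1%, or 0.041 events per subject. 3.71/0.041 = 90.
- High ends of the same four: 3.9 + 9.1 + 1.5 + 5.0 = 19.5%. 3.71/0.195 = 19.
- High ends with the DBS deficit figure (16%) in place of permanent deficit: 3.9 + 9.1 + 16 + 5.0 = 34%. 3.71/0.34 = 10.9.
- That sum doubled for two operations and two connectors: 68%. 3.71/0.68 = 5.5.
- Widest set tried, all high ends: serious skin 5.0, low-to-moderate skin 14.0, bleeding 3.9, infection 9.1, CSF leak 1.4, transient deficit after resection 30, transient deficit with strips 11.1, permanent deficit 1.5 = 76%. 3.71/0.76 = 4.9.

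No set tried brings the end-of-implant limit within a factor of about five.

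**4. How well each reading discriminates.** Take SAE counts as Poisson. A mean of 0.34 is the third sum above; 1.7 is five times that.

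| Mean SAEs | Final rate at or below 1% (three or fewer) | Running breach, SAEs uniform over 371 days | Running breach, all SAEs in first 30 days |
|---|---|---|---|
| 0.34 | > 0.999 | 0.09 | 0.29 |
| 1.7 | 0.91 | 0.44 | 0.82 |

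The last column is 1 - exp(-mean); the uniform column is simulated. The final rate hardly separates the two means. The running rate does so to a useful degree.

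**5. What an observed count supports.** Exact one-sided 95% Poisson upper bounds on 371 days: zero SAEs, -ln(0.05)/371 = 0.81% per day; one SAE, 1.28%; three SAEs, 2.09%. Only zero SAEs puts the bound below 1%. With a two-sided 95% interval, zero SAEs gives -ln(0.025)/371 = 0.994%, but on 364 days it gives 1.013%. The interval and the count of implant-days therefore need fixing in advance.

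**The case against.** The strongest reply is that Table 10-1 specifies a continuous comparison. On that rule the limit is strict after surgery, when one SAE in the first 99 days breaches it. A reader might infer that the endpoint carries almost no safety information. The documents do not support that: it is a fair description of the final rate only, and step 4 shows that the running rate discriminates. What remains is that the plan does not name the deciding reading, and that three late SAEs pass on either.

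A reader might also infer that the limit sits 5 to 90 times above the protocol's own expected SAE rate. There is no such rate. The range depends on which complications are summed. The sums also omit unrelated SAEs, whereas section 8.2.1 defines adverse events regardless of cause and treats any hospitalization for a clinical event as serious. So it cannot be said that the sums overstate what should be expected. Nor is every quoted rate per patient; the denominators are mixed. The narrower statement stands: all are cumulative, none is per day.

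The references cited for the 1% are not available here. They may report event rates over time that justify it, so I do not say the figure misstates them, only that the conversion is not shown.

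Finally, this is a secondary endpoint in a two-subject feasibility study, and section 13.4 disclaims power for conclusions on absolute safety. Section 5.3 also lists serious adverse events as a withdrawal criterion, so a subject with three SAEs may not reach 371 days. Both points lower the stakes. Neither supplies the missing derivation or decision rule.

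**Conclusion.** The point holds in this form. The limit amounts to 3.71 SAEs per subject over 371 days (3.64 over 364). Three SAEs meet the hypothesis at the end of implantation, and can meet it on the running comparison too if they fall late. The rates in section 1.4, summed illustratively, come to about 0.04 to 0.7 events per subject, so the end-of-implant limit is at least about five times higher, and nothing in either document connects the two scales.

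The multiple rests on my choice of categories and excludes unrelated SAEs, so it shows a gap in scale and does not estimate the expected SAE rate. I have read the endpoint's Severe Adverse Event as the serious adverse event of section 8.2.1, the only one of the two terms defined; the wording should be reconciled. The count of 3.71, the day-100 rule and the Poisson bounds need only the stated limit and the implant duration, with a constant event rate assumed for the bounds.

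**What to change.** In Protocol sections 1.5, 2.1, Table 10-1 and 10.1.2:

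- State the limit as the SAE count per subject over the implant period that it represents, with the number of implant-days used.
- Show how that count was derived and reconcile it with the cumulative rates in section 1.4. The sponsor should justify the level; I propose no replacement number.
- State whether the running or the final rate decides the endpoint.

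In the analysis section and the SAP:

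- Report each subject's SAE count, both all-cause and device- or procedure-associated, with implant-days and an exact Poisson interval of stated level and sidedness.
- Claim a rate below 1% per implant-day only if the upper bound is below 1%. With a one-sided 95% bound on 371 days, that means zero SAEs.

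Keeping the all-cause count leaves the endpoint as defined; the associated count is additional and is the closer match to section 1.4. The cost is wording in four protocol places plus a short analysis paragraph, with no new data beyond the SAE and causality records that sections 8.2.3 and 8.2.5 already require. The downside is that the safety statement becomes harder to support: one SAE in a subject would rule out the claim for that subject.
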